4.2 Scientific Rationale for Study Design

The study design selected is deemed optimal for the initial evaluation of safety, tolerability, and PK of MK-5720 in schizophrenic patients.

This is the first instance of administration of MK-5720 to humans with the study aimed to evaluate the safety and tolerability of MK-5720 and characterize the PK profile of MK-5720 as single ascending doses in participants with schizophrenia with the protocol specifically designed in a manner to ensure the safety of the participant. The study incorporates an oral tolerability run-in period with MK-8189 to demonstrate and establish acceptable tolerability with MK-8189 in individual participants prior to administration of MK-5720 IM injection given the inability to reduce daily exposure levels of MK-8189 once MK-5720 injection is administered to participants. Data from the study will be instrumental in guiding dose selection and dosing regimen for future clinical studies. Since the developmental and reproductive toxicological data for MK-5720 has not been generated at this stage, the potential effect of MK-5720 in reproductive healthy women is unknown and hence, only adult men and PONCBP, ages 18 to 60 years of age inclusive, who meet the inclusion criteria are eligible to participate in the study.

The protocol has been designed in a manner to ensure the safety of clinical study participants. In all preclinical studies the bioconversion of prodrug MK-5720 to MK-8189 is rapid and generally similar between monkey and human but found to be more rapid in rat. Following IV administration of MK-5720 in rats and monkeys, the plasma concentration of MK-5720 was undetectable at timepoints beyond 15 minutes postdose. Additionally, the exposure of MK-5720 was less than 1% of the MK-8189 exposure (AUC0-inf) seen after IM administration of MK-5720 in monkeys. The rapid bioconversion prevented determination of t_{1/2} of MK-5720. Given MK-5720 is approximately 650-fold less potent compared to MK-8189 based on in vitro binding assays and that the bioconversion of MK-5720 in humans is anticipated to be rapid, concentrations are expected to be well below pharmacologically active concentrations and therefore, the main pharmacological activity expected in the clinic is as a result of the MK-8189 metabolite. Both, prodrug and MK-8189 concentrations will be actively monitored in the clinic.

Furthermore, the structure of this study is designed based upon the projected PK of MK-8189 derived from MK-5720 LAI, that is estimated to have a t_{1/2} of ~ 10 days in humans. This study will collect PK samples for 55 days postdose to ensure MK-8189 washout of at approximately 5 half-lives.

4.2.1 Rationale for Endpoints

4.2.1.1 Efficacy Endpoints

No efficacy endpoints will be evaluated in this study.

4.2.1.2 Safety Endpoints

No treatment related findings were identified in the GLP 1-month single dose IM toxicity studies with 3-month recovery period conducted with MK-5720 in rats and NHPs. The

NOAELs were the highest dose tested, 510 mg/kg in rats [REDACTED]

[REDACTED] for MK-5720.

Clinical pathology changes were not considered toxicologically meaningful, given the small magnitude and transient nature, and were attributed to an inflammatory response associated with MK-5720 histomorphology changes in the injection sites noted in rats at ≥ 30 mg/kg [REDACTED]

[REDACTED] In both species these findings resolved after a 3-month recovery period. Histological findings at the injection sites in rats and NHPs were consistent with those typically observed following administration of a long-acting formulation that produces an extended-release depot [Paquette SM, et al 2014].

Because studies in preclinical species are not always predictive of what may occur in humans, the safety and tolerability of MK-5720 will be assessed throughout the study by monitoring participants frequently for clinical AEs as well as through the conduct of neurological exams, physical exams, ECGs, VS, and laboratory safety tests (chemistry, hematology, urinalysis). The timing of the safety endpoints has been planned to ensure adequate safety monitoring throughout the treatment period also taking into consideration the range of potential half-life predictions of MK-8189 from the MK-5720 LAI. Key safety data such as VS, 12-lead ECGs, lab safety tests and physical/neurological examinations will be reviewed for up to at least 14-days postdose for Panel A prior to dose escalation to Panel B and up to 28-days postdose prior to dose escalation to the next higher dose level in all other treatment periods. The C-SSRS will be administered to monitor mood and suicidal ideation and behavior in all trial participants (see Section 4.2). In addition, scales will be included to evaluate EPS and general well-being.

As EPS are associated with antipsychotics and have been observed in the MK-8189 clinical program, the BARS, AIMS and SAS will be used to quantify any EPS observed in the study. The BARS is an akathisia rating scale with objective and subjective measures and an overall rating from 0 to 5. A score of 0 presents no evidence for akathisia, a score of 3 is moderate akathisia and a score of 5 is severe akathisia. The AIMS evaluates 12 items and uses a 5-point scale to assess abnormal movement in 3 areas (orofacial, extremities, trunk). The SAS evaluates 10 items and uses a 5-point scale to measure symptoms of parkinsonism or parkinsonian side effects (including rigidity, tremor, akinesia, and salivation).

The BPRS rating scale will be used to measure psychiatric symptoms such as depression, anxiety, hallucinations, and unusual behavior in a range of psychotic and affective symptoms in participants with schizophrenia. The BPRS has been used in clinical research as a tool to measure treatment effects and are effective scales to monitor the general well-being of the psychiatric patients. The BPRS consists of 18 symptom constructs and takes 20 to 30 minutes for the interview and scoring. The rater should enter a number ranging from 1 (not present) to 7 (extremely severe). Zero is entered if the item is not assessed. Participants who experience severe psychosis during the study will be discontinued and referred for additional treatment as indicated.

Rescue medications for the management of EPS side effects and administration of standard of care practice (oral antipsychotics) in the event of worsening of psychosis while on MK-5720 LAI to control symptoms associated with schizophrenia during washout of MK-5720 are detailed in Section 6.5.1.

4.2.1.3 Pharmacokinetic Endpoints

One of the primary objectives of the study is to characterize the PK profile of MK-5720 as well as MK-8189 as rising single doses of administration of the IM MK-5720 LAI in Period 2. In order to characterize the PK profile of MK-5720 and MK-8189, noncompartmental PK parameters, AUC0-last (MK-5720 only), AUC0-inf, AUC0-28d (MK-8189 only), Cmax, C28d (MK-8189 only), Tmax, apparent t1/2, apparent CL/F, and apparent Vz/F will be estimated after single-dose IM administration of the MK-5720 LAI. The dose escalation criteria based on PK analysis are listed below in [Table 2]. Additionally, in Period 1 of the study, one of the exploratory objectives is to characterize the PK profile of MK-8189 following multiple oral doses of MK-8189. Therefore, the noncompartmental PK parameters, AUC0-24, Cmax, Tmax, terminal t1/2 and C24 will be estimated on day 1 and day 7. Plasma samples will be analyzed based on prespecified time point sampling mentioned in Section 1.3.

Table 2 Dose Escalation Criteria Based on PK Analysis

Dose (Panel)	Dose Escalation Decision Criteria
140 mg (C)	28d postdose PK analysis from the preceding doses from Panels A and B
280 mg (D)	28d postdose PK analysis from the preceding dose in Panels C
≤560 mg (E)	28d postdose PK analysis from the preceding dose in Panel D
≤560 mg (F)	28d postdose PK analysis from the preceding dose in Panel E
28d=28 days; PK=pharmacokinetics	

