4.3.1 Starting Dose for This Study

The starting dose of 35 mg is proposed in conformance with the “Guideline on Strategies to Identify and Mitigate Risks for First-in- Human Clinical Trials with Investigational Medicinal Products” [European Medicines Agency 2007] as well as the MRSD calculation [Food and Drug Administration 2005], the MRSD for the first such instance of drug administration in humans is based on NOAEL determined in nonclinical safety studies performed in the most sensitive and relevant animal species adjusted with allometric scaling factors to calculate the HED.

A 4-week, 3-dose level toxicity study was conducted with MK-5720 in rats at (12, 30, 510 mg/kg/day) and rhesus (12, 36, 140 mg/kg/day) to assess the potential toxicity and toxicokinetic profile of MK-5720. No treatment related findings were identified in the GLP 1-month single dose IM toxicity studies with 3-month recovery period conducted with MK-5720 in rats and NHPs. Histological findings at the injection sites in rats and NHPs were consistent with those typically observed following administration of a long-acting formulation that produces an extended-release depot and the inflammatory response associated with MK-5720 histomorphology changes at the injection sites findings were resolved after a 3-month recovery period in both species.

The NOAELs for MK-5720 were the highest dose tested, 510 mg/kg in rats and 140 mg/kg in rhesus. While the NOAEL was the highest dose studied in both species in the 1-month GLP

compliant toxicological study, given the rat provides lower overall exposures for MK-5720 and lower EMs to the projected efficacious dose of MK-5720, rat is determined to be the most sensitive species. Therefore, rat NOAEL Cmax and AUC exposure cap for MK-5720 will be used for the purposes of safety multiple calculations that corresponds to 2.05 $\mu\text{M} \cdot \text{hr}$ and 0.0129 μM plasma exposures for AUC0-28d and Cmax respectively. See [Table 3] for PK exposures of MK-5720 at NOAEL doses in rats and rhesus.

Table 3 Pharmacokinetic Exposures of MK-5720 at NOAEL Doses

Species	Dose (mg/kg)	Cmax (μM)	AUC0-28d($\mu\text{M} \cdot \text{hr}$)
Rat	510	0.0129	2.05
Rhesus	140	0.0713	9.27

AUC0-28d= area under the concentration-time curve from 0 to 28 days, Cmax=maximum plasma concentration

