The calculated HED corresponding to the rat NOAEL adjusted by using an allometric scaling factor is 4957 mg (510 mg/kg x 0.162 [rat to human dose conversion factor] x 60 kg [estimated human adult weight]). The MRSD calculated by applying a safety factor of 10, yields a starting dose of 495 mg. However, a safety factor of 50 has been applied to account for variability in the preclinical to clinical translation of input rate for the LAI. This results in a MRSD of 99 mg based on rat NOAEL (1/50*4957=99 mg) and 54 mg based on rhesus NOAEL (HED=140 mg/kg x 0.324 [rhesus to human dose conversion factor] x 60 kg=2722 mg; 1/50*2722 =54 mg).

The MK-5720 proposed starting dose of 35 mg provides a ~ 1.5- to 2.8-fold safety margin to the MRSD of 54 and 99 mg based on the rhesus and rat NOAEL, respectively. The lowest weight permitted in the study is 50 kg; even for a 50-kg participant the starting dose of 35 mg offers a 1.2-fold safety factor to the more conservative MRSD of 54 mg based on rhesus NOAEL. The 35-mg starting dose is also the lowest possible dose of the LAI that can be administered accurately via the IM route based on a 0.1-mL administration volume.

The starting dose of 35 mg is estimated to yield a human MK-5720 AUC0-28d of 0.09 $\mu\text{M} \cdot \text{hr}$ with a MK-5720 Cmax of 0.00019 μM that is approximately 23- and 68-fold lower than the rat AUC0-28d and Cmax NOAEL exposure cap and 103- and 375-fold lower than the rhesus AUC0-28d and Cmax NOAEL, respectively. CC1

For more detailed information regarding results from the rat and rhesus toxicological studies, please refer to the IB for MK-5720.

[figure not shown]

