and were consistent with findings typically observed after administration of long-acting injectable formulations to rats.

IM injection was considered to be generally well tolerated at all doses (12, 36 and 140 mg/kg) in monkeys in the 1-month GLP toxicological study. There were no test article-related unscheduled deaths, and no test article-related changes in body weight, ECG, ophthalmic, hematology, or urinalysis parameters. By the end of the 1-month toxicity assessment period at doses \leq 140 mg/kg, clinical signs had generally resolved and alterations in serum markers of inflammation (fibrinogen and C-reactive protein) were not considered toxicologically meaningful.

Minimal to moderate chronic inflammation at the IM injection site observed at final necropsy (1-month after injection) was an expected finding typically observed with administration of long-acting formulations in nonhuman primates. At the recovery sacrifice (limited to Cohort B animals in the low- and mid-dose groups), no test article-related gross or histomorphologic findings were observed at the injection site. No foci of chronic inflammation were observed in the quadriceps muscle group. Overall, the injection site reaction in the mid- and low-dose groups was considered to be in either a resolution phase or recovered after a 1-month toxicity assessment and a 3-month treatment-free period.

Based on the presence of test article-related findings at all dose levels, the NOAEL was 140 mg/ as injection sites reactions were not considered adverse, were reversible at the dose levels examined (12 and 36 mg/kg) and were consistent with findings typically observed after administration of long-acting injectable formulations to monkeys.

Since the rat NOAEL provides a \sim 1.4X EM for the AUC0-28d compared to 6.4X EM for the rhesus relative to the highest planned dose of 560 mg of MK-5720 based on the 1-month repeat dose toxicological studies, rat is considered the most sensitive species. Thus, the NOAEL for the purposes of establishing maximum allowable exposures is 2.05 μ M*hr and 0.0129 μ M for AUC0-28d and Cmax, respectively. The highest planned dose of 560 mg of MK-5720 [REDACTED] provides a 4.3-fold safety margin to the rat Cmax NOAEL exposure cap. Furthermore, no MK-5720-related effects on QTc or HR were noted in anesthetized NHPs up to the highest dose tested [REDACTED]

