Maximal MK-5720 LAI single doses of up to 560 mg are proposed in the study to generate safety margins to the 280-mg dose of MK-572 [REDACTED]

Importantly, MK-5720 dose flexibility is built in the study as a contingency in the event resulting MK-8189 plasma concentrations from MK-5720 LAI are lower than that projected due to faster depletion of drug from the LAI or due to differences in LAI input rate observed in the clinic compared to that observed preclinically resulting in sub-efficacious MK-8189 plasma concentrations. MK-5720 LAI doses in the study have been selected in the study to result in MK-8189 plasma concentrations that remain within the clinical experience generated with the oral MK-8189 program in participants with schizophrenia and supported

by having sufficient safety margins at the highest dose proposed based on preclinical safety data generated with MK-5720 and MK-8189.

CCI

The projected MK-5720 exposures corresponding to the highest planned dose of 560 mg of MK-5720 LAI CCI provides a 4.3 and 1.4-fold safety margin to the rat (more sensitive compared to rhesus) MK-5720 C_{max} and AUC NOAEL exposure cap [refer to Section 4.3.1.2 of MK-5720 IB]. Furthermore, the projected MK-8189 C_{max} and AUC_{0-28d} corresponding to the 560 mg-dose of MK-5720 LAI CCI CCI provides a ~15 and 2.5-fold safety margin to the rat MK-8189 C_{max} and AUC NOAEL and ~ 9 and 3.3-fold to the rhesus C_{max} and NOAEL exposure cap, based on the 6 and 9-month repeat dose GLP tox study conducted with oral MK-8189 [refer to Section 4.3.2 of MK-5720 IB]. The projected MK-8189 C_{max} exposures corresponding to the 560- mg dose of LAI (~ 3 μ M) is within the range of the highest MK-8189 mean C_{max} exposure observed with 80-mg dose of oral MK-8189 on Day 2 of ~ 2.63 μ M (95% CI 2.08, 3.32 μ M; preliminary data) that was generally well tolerated in participants with schizophrenia (P014).

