Because studies in preclinical species are not always predictive of what may occur in humans, safety of MK-5720 will be assessed throughout the study by monitoring AEs, physical/neurological examinations, VS, ECGs, and laboratory safety tests (chemistry, hematology, urinalysis). The timing of the safety endpoints has been planned to ensure adequate safety monitoring throughout the treatment period, taking into consideration the range of potential t_{1/2} predictions of MK-5720. Participants will be followed for at least 55 days to allow for adequate MK-5720 washout (~ 5-half-lives based on an estimated t_{1/2} of 10 days for MK-8189 in humans). Safety data from each dosing period will be carefully reviewed before escalation to the next higher dose. Key safety data such as VS, 12-lead ECGs, lab safety tests and physical/neurological examinations will be reviewed for up to at least 14 days postdose (Panel A) and up to 28 days postdose for all other panels prior to dose escalation to the next higher dose level. Plasma concentrations of MK-5720 from the preceding panels will be determined at the allocated PK breaks to ensure that the NOAEL AUC exposure limits are not exceeded at the doses in the subsequent panels. Since this is the first instance of administration of MK-5720 to humans, the dose levels and interval between doses may be adjusted based on safety and/or PK data from the prior periods.

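### Is the MK-5720 exposure cap set on an AUC (AUC0-28d) that the plan never derives for MK-5720?

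*Combined protocol and SAP*

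**What the plan says.** **The cap.** Section 4.3.1 states that the "rat NOAEL Cmax and AUC exposure cap for MK-5720 will be used for the purposes of safety multiple calculations", with values of 2.05 µM·hr for AUC0-28d and 0.0129 µM for Cmax. Section 4.3.2 repeats that "the NOAEL for the purposes of establishing maximum allowable exposures is 2.05" (µM·hr, for AUC0-28d). The sponsor's projections use the same window: "The starting dose of 35 mg is estimated to yield a human MK-5720 AUC0-28d of 0.09" µM·hr. At 560 mg, Section 4.3.2 gives the rat margin as about "1.4X EM for the AUC0-28d compared to 6.4X EM for the rhesus relative to the highest planned dose", and says that this dose "provides a 4.3-fold safety margin to the rat Cmax NOAEL exposure cap".

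**Use of the cap.** Sections 4.1 and 4.3.2 have MK-5720 concentrations determined at the PK breaks "to ensure that the NOAEL AUC exposure limits are not exceeded at the doses in the subsequent panels", without naming the AUC window. Section 4.3.3 names it: MK-5720 is monitored against the AUC0-28d and Cmax cap. Stopping rule 3 (Section 6.6.1) compares mean Cmax or AUC with the maximum defined in Section 4.3.

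**The parameter lists.** Section 4.2.1.3 gives "AUC0-last (MK-5720 only), AUC0-inf, AUC0-28d (MK-8189 only), Cmax, C28d (MK-8189 only". The Synopsis and Sections 3, 9.3.1, 9.3.2 and 9.5.2 follow the same pattern. MK-5720 has AUC0-last, AUC0-inf and Cmax; AUC0-28d appears for MK-8189 alone.

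**The concern.** A safety limit should be checked on the quantity in which it is expressed. Here the limit is a 28-day AUC for MK-5720, while the section on PK endpoints labels that AUC as belonging to the other analyte. Cmax, the looser limit, is in every MK-5720 list; the tighter one is in none. With an AUC margin of about 1.4 at the top dose of a first-in-human study, the choice of window could use up much of the margin. AUC0-last can end at a different time in each participant, and AUC0-inf adds an extrapolated part. What would be at stake is whether the escalation reviews and stopping rule 3 compare like with like, and whether observed exposure can be set against the sponsor's own projection.

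**Working it through.** **1. The plan's margins reproduce, and they are on AUC0-28d.** Inputs: projected 35 mg exposure of 0.09 µM·hr and 0.00019 µM (Section 4.3.1); NOAEL exposures from Table 3.

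- Rat: 2.05/0.09 = 22.8 (stated 23); 0.0129/0.00019 = 67.9 (stated 68).
- Rhesus: 9.27/0.09 = 103; 0.0713/0.00019 = 375.
- 560 mg, assuming dose proportionality (560/35 = 16): AUC0-28d = 16 × 0.09 = 1.44, so rat 2.05/1.44 = 1.42 (stated 1.4) and rhesus 9.27/1.44 = 6.44 (stated 6.4). Cmax = 16 × 0.00019 = 0.00304, so 0.0129/0.00304 = 4.24 (stated 4.3, within the rounding of 0.00019).

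**2. What the escalation reviews see.** Table 2 bases the PK review before each of Panels C, D, E and F on 28-day postdose data, and Section 4.1 says the same. The Period 2 schedule (footnote k) includes a sample at 672 h, and 672/24 = 28 days.

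- If the 672-h sample is measurable, AUC0-last on data cut at 28 days is AUC0-28d.
- If concentrations drop below the assay limit (LLOQ) earlier and stay there, the omitted area is at most LLOQ × (672 − t_last). The documents do not show the LLOQ. If it is assumed to be no higher than the projected 35 mg peak, the omission cannot exceed 0.00019 × 672 = 0.128 µM·hr, and 0.128/2.05 = 6% of the cap. An exposure at the cap has a 28-day mean concentration of 2.05/672 = 0.00305 µM, 16 times that peak. Truncation therefore matters least where the cap is closest.
- Section 4.1 bases the move from Panel A to Panel B on 14 days of safety data. By proportionality, 70 mg gives 2 × 0.09 = 0.18 µM·hr, and 2.05/0.18 = 11.4, too far from the cap for the window to matter.

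**3. What happens on the full data.** Sampling ends at 1320/24 = 55 days. The visible text gives no MK-5720 half-life; I assume the 10 days stated for MK-8189 from the injection (Section 4.3.3).

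- Exponential decline from dosing: AUC0-inf/AUC0-28d = 1/(1 − 2^−2.8) = 1.17; AUC0-55d/AUC0-28d = (1 − 2^−5.5)/(1 − 2^−2.8) = 1.14.
- First-order input with a 3-day half-life: 1.26 and 1.22.
- Shapes solved to match the projected ratio of 28-day mean to Cmax (at 35 mg, (0.09/672)/0.00019 = 0.705): plateau then decline gives 1.20 to 1.21 and 1.17 to 1.18; first-order input and output gives 1.28 to 1.32 and 1.23 to 1.27.
- Linear rise to Day 14, plateau to Day 23, then decline (relative to Cmax, in days): AUC0-28d = 7 + 9 + 14.43 × (1 − 2^−0.5) = 20.23; mean/Cmax = 20.23/28 = 0.72; AUC0-inf = 16 + 14.43 = 30.43; ratio 30.43/20.23 = 1.50.

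A margin of 1.42 would then read between 1.42/1.17 = 1.21 and 1.42/1.50 = 0.95 on AUC0-inf. In each case the substitute makes exposure look closer to the cap than it is.

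**The case for a change.** The best case for a change is that the label in Section 4.2.1.3 is an active restriction, not an omission; that it is repeated across the endpoint and analysis sections; and that agreement between AUC0-last and AUC0-28d at the reviews comes from the data cut-off and is not specified. The amendment would also be cheap: one further noncompartmental parameter and a few words.

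The mismatch stands as a matter of wording. The rest does not carry the point:

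- The list in Section 4.2.1.3 serves to characterise the PK profile. The cap check is a separate activity with its own text, and Section 4.3.3 names AUC0-28d there. Section 9.6 allows PK summaries as needed for escalation meetings and does not confine them to the endpoint parameters. An analyst told to compare with a 28-day cap will compute a 28-day AUC.
- No visible passage plans a comparison of final 55-day exposure with the cap, or of AUC0-inf with it. If one is wanted, the 672-h sample makes AUC0-28d computable.
- Removing the label from Section 4.2.1.3 alone would put that list out of step with the primary endpoints in the Synopsis and Sections 3 and 9.3.1, which it now mirrors.
- Text near the cap is redacted, so the absence of a derivation can be asserted only for the visible wording.

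**Conclusion.** No change to the plan follows. This is a gap in wording that the plan's own cross-references fill: Section 4.3 defines the metric, Section 4.3.3 says it is the one monitored, and stopping rule 3 points back to Section 4.3. At the 28-day reviews that govern Panels C to F, the listed AUC0-last and the capped AUC0-28d agree, apart from any part below quantification. On the assay-limit assumption above, that part is at most 6% of the cap.

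On longer data the listed AUCs run high and so err toward caution. The amount (AUC0-inf 1.17 to 1.50 times AUC0-28d) is illustrative: it rests on a half-life stated for MK-8189, and the shapes tried do not bound it. If MK-5720 becomes unmeasurable before Day 28, AUC0-last shows no such inflation.

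The conclusion depends on the PK reviews using 28-day data, as Table 2 and Section 4.1 require. Given that, adding MK-5720 AUC0-28d to the lists would alter no escalation decision and no planned result.
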